4. STUDY DESIGN

This is a single-center, observer-blinded, Phase 1, dosage-escalation trial to evaluate the safety, tolerability, reactogenicity, and immunogenicity of ChAd155-RG compared with RABAVER in rabies virus-naïve healthy male and non-pregnant female adult subjects. There are 4 dose groups (see Table 1).

Subjects who have never received a licensed or investigational rabies virus vaccine, or an Ad-based investigational vaccine, and who have never been exposed to a rabid animal will be eligible for enrollment.

Since this is a dosage-escalation study, sentinel subjects will be used at each dosage level. The first four subjects will be randomized to Group A or D and will receive either a single dose of ChAd155-RG at the lower dosage (5×10^{10} vp, N=3) (followed by placebo on Days 8, 15, and 22) or RABAVER (N=1) (on Days 1, 8, and 22, and placebo on Day 15) (see Table 1). These subjects will be monitored for safety, tolerability, and reactogenicity through day 7 after first study vaccination, and if no pre-defined halting rule is met (Section 9), then four additional sentinel subjects will be randomized to Group B or D and will receive either a single dose of ChAd155-RG at the higher dosage (1×10^{11} vp, N=3) (followed by placebo on Days 8, 15, and 22) or RABAVER (N=1) (on Days 1, 8, and 22, and placebo on Day 15) (see Table 1). These subjects will be monitored for safety, tolerability, and reactogenicity through day 7 after first study vaccination. The SMC will then review the available safety, reactogenicity, AE, and lab data of all the sentinel subjects, and will decide if the remaining non-sentinel subjects should be enrolled.

If the SMC recommends proceeding with the remainder of trial enrollment, eligible individuals will be enrolled and randomized to one of the four dose groups (Groups A-D). To maintain blinding of study personnel conducting surveillance and assessment of AEs, subjects in these groups will receive 4 sequential injections, 1 ml per injection, in alternating arms, on the same schedule:

- Subjects randomized to Group A will receive ChAd155-RG at the lower dosage (5×10^{10} vp) on Day 1, then placebo injections on Days 8, 15, and 22
- Subjects randomized to Group B will receive ChAd155-RG at the higher dosage (1×10^{11} vp) on Day 1, then placebo injections on Days 8, 15, and 22

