Visually inspect the ChAd155-RG Vaccine, RABAVERT Vaccine, and admixture vials, upon receipt and before use. If the vaccine(s) appear(s) to be damaged, contaminated, or discolored, contain visible particulate matter, or if there are any concerns regarding its integrity, do not use the affected vaccine(s). Instead, quarantine it at the correct storage temperature and label it "Do Not Use" (until further notice). The site PI or responsible person should immediately contact the DMID Product Support Team at [contact] and DMID CPM for further instructions before any additional vaccines are administered. Based on the information collected, DMID and/or the manufacturer will determine whether the affected vaccine(s) or admixture can be used. If it cannot be used, the site will receive specific final disposition instructions from DMID (e.g. how to return the affected vaccine(s) to DMID CMS or destroy it on site). If the vaccine(s) or admixture is unusable, the site pharmacist will prepare another dose

of admixture vial. Replacement vials may be requested by contacting DMID. Additional instructions for quarantine and DMID contact information are provided in the MOP.

Study vaccine administration will be performed by an unblinded vaccine administrator who is credentialed to administer vaccines, but will not participate in dose preparation, and may not be involved in study-related assessments, subject contact, or data collection after vaccine administration. On the assigned dosage days, each dose of vaccine will be administered to subjects via a single IM injection (depending on group assignment and/or randomization) in the preferred arm. The dose administration schedule is as follows:

- Subjects randomized to Group A will receive ChAd155-RG at the lower dosage (5×10^{10} vp) on Day 1, then placebo injections on Days 8, 15, and 22
- Subjects randomized to Group B will receive ChAd155-RG at the higher dosage (1×10^{11} vp) on Day 1, then placebo injections on Days 8, 15, and 22
- Subjects randomized to Group C will receive ChAd155-RG at the higher dosage (1×10^{11} vp) on Days 1 and 15, and placebo injections on Days 8 and 22
- Subjects randomized to Group D will receive RABAVERT at the standard dose (1mL) on Days 1, 8, and 22, and a placebo injection on Day 15

Placebo

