7.4.2. Visit 03, Day 8 (window: +2 days), Second Vaccination

- If a subject has a positive symptom screen prior to the visit (per the MOP), viral testing may be performed during this study visit with a research-based assay
- Obtain interim medical history, including an assessment for new medical conditions by interview of subjects and note any changes since the previous clinic visit or phone call.
- Review eligibility criteria with subjects, and review results of all safety lab evaluations, before vaccination to assure continued eligibility for vaccination.
- Record all concomitant medications on the appropriate eCRF.
- Perform a targeted physical examination, if indicated based on review of complete medical history.
- Obtain vital signs including oral temperature, blood pressure, and pulse.
- Examine vaccination site for local reactions and determine information recorded by subjects on the memory aid conforms to examination.
- Collect blood for safety labs (chemistry, hematology), immunogenicity (RFFIT assay), and developer assays before vaccination.
- Perform a urine pregnancy test within 24 hours before second vaccination on all female subjects of childbearing potential. Results must be negative and known before second vaccination.
- Perform pre-administration reactogenicity assessments before the second vaccination to establish baseline. Subjects will then receive a single dose of vaccine via IM injection into the deltoid muscle of the arm opposite to that of the first injection. The site of injection (right or left arm) and time of administration will be recorded on the appropriate eCRF.
- Observe subjects in the clinic for ≥ 30 minutes after vaccination to monitor for any acute reactions.
- Evaluate the vaccination site and assess for reactogenicity and AE/SAEs for ≥ 30 minutes after vaccination and before discharge from clinic and record on the appropriate CRF.

- Subjects will enter their reactogenicity information on a memory aid. Subjects will be provided a thermometer, ruler and memory aid and will record daily oral temperature, solicited injection site and systemic reactions, any unsolicited AEs, and concomitant medications. Subjects will be asked to bring their memory aid with them at their next study visit.
- Assess all AE/SAEs and new onset chronic medical conditions and record them on the appropriate eCRF.

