- A Grade 3 solicited systemic AE of fatigue, malaise or headache considered to be related to the study vaccines, that does not resolve or decrease to a lower grade within 2 days.
- Female subject becomes pregnant
- Subject develops a new illness or condition that meets the Exclusion Criteria
- Subject develops a new medical condition or medication change for which continued participation, in the opinion of the investigator, would pose a risk to the subject, would interfere with the subject's ability to complete this trial, or would be likely to confound interpretation of the results
- Subject is no longer willing and/or able to adhere to study restrictions outlined in the Inclusion and Exclusion Criteria

- Subject has a fever (defined as an oral temperature $\geq 38.0^{\circ}\text{C}$) or an acute illness at the time of boost vaccination administration. The next study vaccination can be deferred until the fever or illness resolves or only minor residual symptoms remain, that in the opinion of the investigator, will not interfere with the ability to assess safety parameters as required by the protocol, provided that the boost is given within the protocol-defined study window. Permission to administer vaccination outside the protocol-defined study window must be obtained from DMID Medical Officer
- Subject has a Grade 2 or greater solicited injection site or systemic AE at the time of boost vaccination administration. The next study vaccination can be deferred until the AE resolves or decreases to a lower grade, such that in the opinion of the investigator, it will not interfere with the ability to assess safety parameters as required by the protocol, provided that the boost is given within the protocol-defined study window

Note: In case the boost vaccination is postponed, the timing of the safety/immunogenicity visits post-boost will be planned relative to actual vaccination day.

Halting Rules for Discontinuing Further Enrollments and Vaccinations Across this Trial

If one or more of the following halting rules is met, further enrollment and vaccinations will be withheld until the SMC reviews the safety data:

- If any subject experiences anaphylaxis, laryngospasm, bronchospasm within 24 hours after study vaccination
- If two or more subjects experience an allergic reaction (e.g. generalized urticaria) within 3 days after study vaccination
- If any subject experiences injection site ulceration, abscess, or necrosis judged to be related to study vaccine

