## 3.3. Study Definitions and Derived Variables

Seroconversion is defined as a VNA concentration  $\geq 0.5$  IU/mL. Peak GMT is defined as the highest GMT measured across all post-vaccination antibody time points per subject.

The baseline value will be defined as the last value obtained prior to the first vaccination.

Vaccination group is defined as the four vaccine and dose combinations:

- Low Dose ChAd155-RG
- High Dose ChAd155-RG (x1)
- High Dose ChAd155-RG (x2)
- RABAVERT

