### 9.3.1. **Solicited Events and Symptoms**

Solicited local and systemic adverse events were collected prior to each vaccination, 30 minutes post-vaccination and through 7 days after each vaccination. Systemic events include: feverishness, fatigue, malaise, myalgia, arthralgia, headache, nausea, and fever (based on temperature). Local injection site events include: pain, tenderness, pruritis, ecchymosis (grade and measurement), erythema (grade and measurement) and induration (grade and measurement). See [Table 7](#), [Table 8](#), [Table 9](#), and [Table 10](#) for grading details. Each solicited AE will be summarized separately for each vaccination and over all vaccinations, by vaccination group. For ecchymosis, erythema, and induration, the severity based on measurement will be presented separately.

The proportion of subjects (and exact 95% CI) reporting at least one solicited AE over each post-vaccination follow-up period will be summarized for each solicited AE, any systemic symptom, any local symptom, and any symptoms ([Table 31](#), [Table 32](#), [Table 33](#), [Table 34](#), and [Table 35](#)). The 95% CI will be calculated using Clopper-Pearson methodology from a binomial distribution (SAS Proc Freq with a binomial option).

Solicited local injection site and systemic AEs will also be summarized by symptom, dose group, severity, and individual time point (pre-dose, 30 mins post-dose, days 1 to 8). These results will be displayed by dose and dose group in [Table 36](#) through [Table 65](#).

Bar graphs representing the percent of subjects with solicited systemic AEs by dose group, post-vaccination time point, and maximum severity will be presented in [Figure 10](#), [Figure 11](#), [Figure 12](#), [Figure 13](#), and [Figure 14](#). Similar graphs will be presented for solicited local AEs in [Figure 15](#), [Figure 16](#), [Figure 17](#), [Figure 18](#), and [Figure 19](#).

Solicited AEs by subject will be presented in [Listing 11](#) (systemic symptom) and [Listing 12](#) (local symptom).

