**14.3.1.1      Solicited Adverse Events****Table 31:      Number and Percentage of Subjects Experiencing Solicited Adverse Events by Symptom, Maximum Severity, and Vaccination Group - Post Dose 1**

Symptom/ Severity	Low Dose ChAd155-RG (N=X)		High Dose ChAd155-RG (x1) (N=X)		High Dose ChAd155-RG (x2) (N=X)		Combined High Dose ChAd155-RG a (N=X)		RABAVERT (N=X)		All Subjects (N=X)	
	n (%)	95% CI	n (%)	95% CI	n (%)	95% CI	n (%)	95% CI	n (%)	95% CI	n (%)	95% CI
Any Symptom												
Any Severity	x (xx)	xx, xx										
None												
Mild												
Moderate												
Severe												
Repeat for:												
Any Systemic Symptom												
Feverishness												
Fatigue												
Malaise												
Myalgia												
Arthralgia												
Nausea												
Headache												
Fever												
Any Local Symptom												
Pain												
Tenderness												
Pruritis												
Ecchymosis Grade												
Ecchymosis Measurement												
Erythema Grade												
Erythema Measurement												
Induration Grade												
Induration Measurement												
Note: N = Number of subjects in the Safety Population who received the specified dose. Severity is the maximum severity reported over all solicited symptoms post dosing for each subject; n = Number of subjects reporting event.												
a Both high dose groups combined.												

**Table 32: Number and Percentage of Subjects Experiencing Solicited Adverse Events by Symptom, Maximum Severity, and Vaccination Group - Post Dose 2**

Symptom/ Severity	Low Dose Placebo (N=X)		High Dose (x1) Placebo (N=X)		High Dose (x2) Placebo (N=X)		All Placebo a (N=X)		RABAVERT (N=X)		All Subjects (N=X)	
	n (%)	95% CI	n (%)	95% CI	n (%)	95% CI	n (%)	95% CI	n (%)	95% CI	n (%)	95% CI
Any Symptom												
Any Severity	x (xx)	xx, xx										
None												
Mild												
Moderate												
Severe												
Repeat for:												
Any Systemic Symptom												
Feverishness												
Fatigue												
Malaise												
Myalgia												
Arthralgia												
Nausea												
Headache												
Fever												
Any Local Symptom												
Pain												
Tenderness												
Pruritis												
Ecchymosis Grade												
Ecchymosis Measurement												
Erythema Grade												
Erythema Measurement												
Induration Grade												

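### Tables 32 to 34 ignore the pre-dose grade, so a mild symptom persisting from an active dose is counted again under the next injection, which is usually saline

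*SAP*

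**What the plan says.** **Collection.** Protocol 7.4.2 instructs staff to "Perform pre-administration reactogenicity assessments before the second vaccination to establish baseline". The visits for the first, third and fourth injections (7.3.1, 7.4.3, 7.4.5) carry the same instruction.

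**Counting.** SAP 9.3.1 says that the proportion of subjects "reporting at least one solicited AE over each post-vaccination follow-up period will be summarized", with an exact interval, in Tables 31 to 35. The notes to those tables add: "Severity is the maximum severity reported over all solicited symptoms post dosing for each subject". No condition refers to the grade recorded just before the injection. The only baseline the SAP defines is in 3.3: "The baseline value will be defined as the last value obtained prior to the first vaccination".

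**Where pre-dose data appear.** Tables 36 to 65 summarise symptoms by "individual time point (pre-dose, 30 mins post-dose, days 1 to 8". Listings 11 and 12 show the pre-dose assessment, the product received and whether a symptom was ongoing after Day 8.

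**Dosing with a symptom present.** Protocol 9.5 lists, among the reasons to withhold or defer a later dose: "Subject has a Grade 2 or greater solicited injection site or systemic AE at the time of boost vaccination administration". Deferral can end when the grade falls. Protocol 8.1 tolerates a Grade 1 pre-administration symptom, in wording that refers to enrolment.

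**Arm.** Protocol 4 says "subjects in these groups will receive 4 sequential injections, 1 ml per injection, in alternating arms, on the same schedule". SAP 4.1 agrees, and the later vaccination visits in Protocol 7.4 specify the arm opposite to the previous injection. Protocol 6.2 says "each dose of vaccine will be administered to subjects via a single IM injection (depending on group assignment and/or randomization) in the preferred arm", and its placebo paragraph also names the preferred arm.

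**The concern.** Solicited reactogenicity after each vaccination is the first primary endpoint, and it is to be summarised separately for each vaccination. The schedule puts an injection on Days 1, 8, 15 and 22 in every group, and the by-day tables run from Day 1 (the day of vaccination) to Day 8. For a subject seen on the planned day, the last day of follow-up for one dose is therefore the first day of the next, and no rule says which dose owns that day.

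A Grade 1 headache that began after ChAd155-RG on Day 1 and is still present after the Day 8 injection counts as an event after Dose 1 and again after Dose 2. In Groups A, B and C the second event sits in a column headed placebo. What is at stake is how the per-dose rates read: saline columns can contain vaccine symptoms, and part of an active dose's reaction can be shown under a different injection.

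**Working it through.** The documents give no sample size, power or event rate that depends on this point, so there is no stated figure to reproduce. The check is a count from the design, followed by an illustration of size.

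**1. Injections that directly follow an active dose.** Group sizes are from SAP 5 and the sequences from SAP Table 1 (V = active vaccine, P = saline).

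| Group | N | Doses 1–4 | Dose 2 after V? | Dose 3 after V? | Dose 4 after V? |
|---|---|---|---|---|---|
| A | 14 | V P P P | 14, saline | no | no |
| B | 14 | V P P P | 14, saline | no | no |
| C | 10 | V P V P | 10, saline | no | 10, saline |
| D | 12 | V V P V | 12, RABAVERT | 12, saline | no |

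- All such injections: 50 + 12 + 10 = 72.
- Saline among them: 38 + 12 + 10 = 60, and 60/72 = 83%.

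**2. Which tables can be affected.**

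- Table 31 (Dose 1): there is no prior study dose, so no carry-over from one.
- Table 32 (Dose 2): all 38 subjects in the All Placebo column, plus Group D's 12 second RABAVERT doses. One subject is 1/38 = 2.6 points of All Placebo.
- Table 33 (Dose 3): Group D's 12 saline injections. One subject is 1/12 = 8.3 points of that column.
- Table 34 (Dose 4): Group C's 10 saline injections. One subject is 1/10 = 10 points of that column.
- Table 35 (any dose): one maximum per subject over all doses, so a persisting symptom adds no second count.

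**3. Possible size in Table 32, for fatigue.** Protocol 2.3.1 reports fatigue in 50% of high-dosage recipients in an earlier ChAd155 trial. That dosage, 5×10^10 vp, is this trial's lower dosage; the rate at 1×10^11 vp is not given, so 50% for all 38 subjects is an assumption. The fraction r still present at Grade 1 after the Day 8 injection is not in the documents either.

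Carried-over share c = 0.50 × r; subjects carried over = 38 × c. If a share p0 would report fatigue after saline anyway, independently, the tabulated rate is 1 − (1 − p0)(1 − c). The p0 of 10% below is also an assumption.

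| r (assumed) | c | 38 × c | Rate if p0 = 10% |
|---|---|---|---|
| 0% | 0% | 0 | 10.0% |
| 2% | 1% | 0.4 | 10.9% |
| 10% | 5% | 1.9 | 14.5% |
| 20% | 10% | 3.8 | 19.0% |

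At c = 10%, the tabulated rate is 14.5% if p0 = 5% and 28.0% if p0 = 20%. With a new-or-worsened rule it would return to about p0.

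**The case against.** Several arguments against the point have force.

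- **The SAP follows the endpoint as written.** The endpoint is a time window from each vaccination through Day 7 and does not ask for new or worsened symptoms. This stands: the raw count is a legitimate display and should stay.
- **Pre-dose data are reported.** A reader of Tables 31 to 35 alone might infer that the pre-dose assessment is discarded. It is not, since it appears in Tables 36 to 65 and Listings 11 and 12. However, the by-day tables give separate counts per time point and do not link a subject's pre-dose grade to the post-dose grade. The listings allow the link but give no rate or interval.
- **Saline is not a planned reference.** A reader might infer that carry-over biases the primary comparison. SAP 4.2 names RABAVERT as the active control and gives blinding as the purpose of the placebo injections. The whole-regimen display for ChAd155-RG against RABAVERT is Table 35, which carry-over does not inflate. The stronger reading is not supported.
- **Persistence may be rare.** Protocol 2.3.1 says that most AEs in the ChAd3 Ebola vaccine trials resolved within 48 hours. This stands, and is why the range in the working starts at zero.
- **Carry-over is bounded in kind.** The Grade 2 criterion in Protocol 9.5 leaves mainly Grade 1 symptoms. Under alternating arms, a local reaction at the old site can be told apart from one at the new site.
- **A new-or-worsened rule can lose true reactions.** A Grade 1 symptom that resolves and returns at Grade 1 after an active dose would be dropped. This stands as a reason to add such a count and not to replace the raw one.

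**Conclusion.** The point holds for Tables 32 to 34. They take no account of a per-dose baseline that the protocol has staff collect, so a persisting mild symptom is counted under two injections. In 60 of the 72 injections where this could follow directly from an active dose, the second count falls under saline. The main exposure is Table 32, where every subject in the All Placebo column received ChAd155-RG a week before.

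The size cannot be derived from the documents. For fatigue it runs from 0 to about 4 of 38 subjects, assuming 50% incidence and 0 to 20% persistence; the lower part of that range is plausible. No sample size, interval method or comparison against RABAVERT over the whole regimen changes. This is a gap in how per-dose rates are attributed, not an error in the endpoint.

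The arm text is a separate contradiction. It does not show that local carry-over will occur, but whether a local reaction can be assigned to a dose depends on it, and Protocol 9.2.1 treats solicited injection-site events in the reporting period as related.

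**What to change.** 1. Keep the raw counts in Tables 32 to 34. Add a parallel count, with exact 95% interval, of subjects whose post-dose symptom is new or of higher grade than that dose's own pre-dose grade. Compare local events at the same injection site. This extends the rule in Protocol 9.2.1, under which a condition present at screening becomes an AE only if its severity increases.
2. State in SAP 9.3.1 that an entry on the next injection day belongs to the earlier dose only if it was made before that injection.
3. Leave Tables 36 to 65 as they are.
4. Reconcile Protocol 6.2 with Protocol 4, Protocol 7.4 and SAP 4.1 on the injection arm.

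Items 1 and 2 are SAP derivations on data already scheduled for collection. The cost is extra rows or one sensitivity table per dose. The added count may miss a Grade 1 symptom that resolves and recurs, which should be said in the table note.
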